#### 8.1.2. Temporary Discontinuation from Study Treatment

Not applicable.

#### 8.1.3. Discontinuation of Inadvertently Enrolled Subjects

If the sponsor or investigator identifies a subject who did not meet enrollment criteria and was inadvertently enrolled, then the subject should be discontinued from study treatment, unless there are extenuating circumstances that make it medically necessary for the subject to continue on study treatment. If the investigator and Lilly CRP agree it is medically appropriate to continue, the investigator must obtain documented approval from Lilly CRP to allow the inadvertently enrolled subject to continue in the study with or without treatment with Basaglar. Safety

follow-up is as outlined in Section 2 (Schedule of Activities), Section 9.2 (Adverse Events), and Section 9.4 (Safety) of the protocol.

## 8.2. Discontinuation from the Study

Subjects will be discontinued from the study in the following circumstances:

- enrollment in any other clinical study involving an investigational product or enrollment in any other type of medical research judged not to be scientifically or medically compatible with this study
- participation in the study needs to be stopped for medical, safety, regulatory, or other reasons consistent with applicable laws, regulations, and good clinical practice
- investigator decision
  - the investigator decides that the subject should be discontinued from the study
  - if the subject, for any reason, requires treatment with another therapeutic agent that has been demonstrated to be effective for treatment of the study indication, discontinuation from the study occurs prior to introduction of the new agent
  - if the subject has persistent hypoglycemia or increased risk of hypoglycemia
- subject decision
  - the subject or the subject's designee requests to be withdrawn from the study

Subjects discontinuing from the study prematurely for any reason should complete AEs and other safety follow-up per Section 2 (Schedule of Activities), Section 9.2 (Adverse Events), and Section 9.4 (Safety) of this protocol.

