Procedure	Screening	Treatment Period							Follow-up	Notes
Visit	1	2	3	4	5	6 a	7 a	8	9/ET	
Week of Study	-2	0	4	8	12	16	20	24	28	
Allowable Deviation +/- (days)		3	7	7	7	7	7	7		
Self-titration training c		X	X	X	X	X	X	X		This training is given at baseline and reinforced at every visit of the treatment period
Dispense study diary	X	X								Pretreatment study diary will be dispensed at Visit 1 and comprehensive study diary will be dispensed at Visit 2
Dispense study drug		X	X	X	X					
Review study diary		X	X	X	X			X		Pretreatment study diary will be collected at Visit 2 and comprehensive study diary will be collected at Visit 8
Collect unused study drug			X	X	X			X		
Dispense glucometer	X									
Compliance to study drug administration		X	X	X	X	X	X	X		
Adjust insulin dose (if required)			X	X	X			X		Site personnel will review the Basaglar dose and FBG levels recorded in the subject diary. They may recommend change in dose of Basaglar if required.

Abbreviations: AE = adverse event; CV = cardiovascular; DBP = diastolic blood pressure; ECG = electrocardiogram; ET = early termination; FBG = fasting blood glucose; HbA1c = glycated hemoglobin; HIV = human immunodeficiency virus; ITSQ = Insulin Treatment Satisfaction Questionnaire; PR = pulse rate; SAE = serious adverse event; SBP = systolic blood pressure; SMBG = self-monitored blood glucose; WCBP = women of child-bearing potential.

- a Telephone visit.
- b All vital signs should be recorded in the subject in a resting state. If there is a suspicion of postural hypotension or autonomic instability, the investigators at their discretion might decide to record the blood pressure in a supine state and then after standing for 2 minutes to detect any postural hypotension. Blood pressure measurements should be done in the left arm with sphygmomanometer held at the level of the heart. Blood pressure recording in both arms is at the investigators' discretion in selective cases of pulse volume inequality or pulse being absent in either of the arms.
- c Subjects will be instructed to daily measure the FBG levels mandatorily using glucometer before the morning meal till Week 12 and record in the subject diary. Also, subjects will be instructed to measure and record the blood glucose levels using glucometer if they have symptoms of hypoglycemia (including nocturnal hypoglycemia) at any time of the day or night.

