### Follow-up Visit (Week 28)

All subjects will have a follow-up visit 4 weeks after the last dose of Basaglar. Assessments at this visit will be done as detailed in Section 2. Subjects who withdraw from the study will also have assessments done similar to those at the follow-up visit.

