### 9.1. Efficacy and Safety Assessments

#### 9.1.1. Primary Safety Assessments

##### Hypoglycemia

Information on treatment-emergent hypoglycemic events starting from Visit 2 until the last study visit (Visit 9 or early termination [ET] visit) will be collected. Subjects will be trained about signs and symptoms of hypoglycemia. Subjects will be trained to check and record their blood glucose levels if they experience symptoms suggestive of hypoglycemia. For each hypoglycemic event, subjects should record the following data in the study diaries provided by the sponsor via the investigator:

- blood glucose levels
- associated symptoms
- treatment, and
- other pertinent information.

A hypoglycemic event is defined as any time a subject feels that he or she is experiencing a sign or symptom that is associated with hypoglycemia or has a FBG level of  $\leq 54$  mg/dL (3.0 mmol/L), even if it was not associated with signs, symptoms, or treatment consistent with current guidelines.

**Severe hypoglycemia:** An event requiring assistance of another person to actively administer carbohydrates or glucagon or taking other corrective actions. Blood glucose concentrations may not be available during an event, but neurologic recovery following the return of blood glucose to normal levels is considered sufficient evidence that the event was induced by a low blood glucose concentration.

**Nocturnal hypoglycemia:** Any total hypoglycemic event that occurs after bedtime and prior to the first meal in the morning.

**Documented symptomatic hypoglycemia:** An event during which typical symptoms of hypoglycemia are accompanied by a blood glucose level of  $\leq 54$  mg/dL ( $\leq 3.0$  mmol/L) as confirmed by blood glucose measurement.

**Asymptomatic hypoglycemia:** Any event not accompanied by typical symptoms of hypoglycemia but a measured a blood glucose level of  $\leq 54$  mg/dL ( $\leq 3.0$  mmol/L) was observed.

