### 10.2. Populations for Analyses

For purposes of analysis, the following populations are defined:

Population	Description
Enrolled	All participants who sign informed consent form
Full Analysis Set (FAS)	All enrolled participants who take at least 1 dose of study treatment
Safety	Identical to FAS, as no randomization occurs (single arm trial)
Per Protocol Set (PPS)	All FAS subjects, who also meet the following criteria: a) have no violations of inclusion/exclusion criteria b) have not discontinued from the study prior to 24 weeks c) have not been off study medication for more than 14 consecutive days during the treatment period d) have not received chronic (lasting longer than 14 consecutive days) systemic glucocorticoid therapy (excluding topical, intra-articular, intra-ocular, and inhaled preparations)

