6.3 Per-Protocol Analysis Set (PPS)

This analysis population will include all FAS subjects, who also meet the following criteria:

- a) Have no violations of inclusion/exclusion criteria
- b) Have not discontinued from the study prior to 24 weeks
- c) Have not been off study medication for more than 14 consecutive days during the treatment period
- d) Have not received chronic (lasting longer than 14 consecutive days) systemic glucocorticoid therapy (excluding topical, intra-articular, intra-ocular, and inhaled preparations)
 - Set to 'Y' if
 1. For all FAS subjects = "Y" and

- Date of completion/discontinuation is not less than date of visit 8 (week 24)
- 3. within a subject there is no DV.DVCAT = "MAJOR"

CONFIDENTIAL CS.BS.01.00 TPL-1.0: Statistical Analysis Plan Template

Page 19 of 85

7. General considerations

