8.2 Missing data

- Vital Signs: we will use the last observation carry forward (LOCF) method for the missing values.
- 2) Actual and Change from Baseline HbA1c: For subjects requiring rescue medication, HbA1c values recorded after the first administration of rescue medication will not be considered for analysis, and these values will be considered as missing. In addition, for the actual value and change from baseline, a descriptive analysis using LOCF will be performed, using the baseline or 12-week value, if the 24-week value is missing or occurred after use of rescue medication.
- 3) Subjects Reaching HbA1c Targets (≤6.5% and <7%) at Week 24: The HbA1c values used to calculate this binary variable will be the LOCF value, that is, in case the Week 24 value is missing, the Week 12 value will be used. The denominator will be the total FAS population. Subject with missing HbA1c data at Week 12 and Week 24 will be considered as not having reached the target.

For other efficacy parameters 7-point SMBG levels (mg/dL and mmol/L), body mass index (kg/m²), body weight (kg), basal insulin dose (U/day and U/kg/day) we will apply the LOCF method for missing data.

4) ITSQ score: If an item score is missing for a subject and ≤20% of the items within the domain (or overall) are missing for that subject, then the mean of the items scores in the domain (or overall) will be imputed for the missing item score(s). If there are >20% missing items, the individual subject domain (or overall) score will be set to missing. that is here we will use the mean imputation method.

Page 25 of 85

Change at Week 24 from Week 4 for ITSQ score (Transformed overall and domain scores): we will use the last observation carry forward (LOCF) method for the missing values.

5) Laboratory data: we will use the last observation carry forward (LOCF) method for the missing values.

For all other cases the missing data will not be imputed for this trial.

9. Output presentations

This is single arm study; we are not doing any stratification we will present the summary table for single treatment group i.e. Basaglar.

The Section 23, Appendix 1 describe the format and content for presentation of tables, listings and figures (TLFs).

All percentages (%) for a specific summary are calculated using the total number of participants included in the relevant analysis population as the denominator, unless otherwise specified.

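### SAP 19.1.1 ends the primary event window at the Visit 8 date and gives no end date for subjects who leave before Visit 8, so their recorded hypoglycaemic events can drop out of the numerator

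*Protocol*

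**What the plan says.** **Who is counted.** The FAS is defined in Protocol 10.2 as "All enrolled participants who take at least 1 dose of study treatment". SAP Section 9 has percentages "calculated using the total number of participants included in the relevant analysis population as the denominator". A treated subject who leaves early therefore stays in the denominator.

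**What is counted.** SAP 19.2.1 reports the number and percentage of subjects with at least one event from Day 0 to Week 24, with a Clopper-Pearson interval. SAP 19.1.1 requires a glucose of 54 mg/dL or less for both symptomatic and asymptomatic events. It also requires the event to start no earlier than the Visit 2 date and no later than the Visit 8 date. SAP 20.1.3 repeats this window for the nocturnal, severe, documented symptomatic and asymptomatic incidences. It allows the longer window, to the Visit 9 date, for rates only.

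**What is collected from leavers.** Protocol 9.1.1 says that information on hypoglycaemic events "starting from Visit 2 until the last study visit (Visit 9 or early termination [ET] visit) will be collected". Protocol 5.1.1 adds: "Subjects who withdraw from the study will also have assessments done similar to those at the follow-up visit". In the Schedule of Activities that visit is the column headed 9/ET, not Visit 8.

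**How many leave, and why.** Protocol 5.2 assumes 20% drop-out, from 250 enrolled to 200 completers. One of the investigator's grounds in Protocol 8.2 applies "if the subject has persistent hypoglycemia or increased risk of hypoglycemia". Protocol 7.6 also treats significantly non-compliant subjects as withdrawn.

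**Missing data.** SAP 8.2 lists the variables to be imputed. Hypoglycaemia is not among them, and the section closes: "For all other cases the missing data will not be imputed for this trial".

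**The concern.** The upper end of the event window is a visit date that an early leaver may not have. The SAP does not say what happens to the date test in that case. If the test is programmed as written, the comparison with an absent date is not met, and the event is not selected. The subject then counts in the denominator and not in the numerator, although the event was recorded and met the glucose criterion.

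This affects the only primary endpoint of a study whose stated purpose is to assess the risk of hypoglycaemia. The error runs in one direction, towards a lower incidence, and the confidence interval does not reflect it. It is not confined to a rare kind of subject. It applies to anyone without a Visit 8 date, whatever the reason for leaving, and one permitted reason is hypoglycaemia itself.

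**Working it through.** **1. The rules applied to one hypothetical subject.** The subject takes the first dose at Visit 2, records a glucose of 54 mg/dL or less in Week 6, and leaves in Week 8.

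- The reading is likely to exist. Schedule of Activities footnote c says: "Subjects will be instructed to daily measure the FBG levels mandatorily using glucometer before the morning meal till Week 12". Glucose is also checked whenever there are symptoms.
- The event is collected (Protocol 9.1.1) and the subject is in the FAS (Protocol 10.2, SAP 6.2).
- The glucose criterion in SAP 19.1.1 is met, and so is the lower date limit (Visit 2).
- The upper date limit is the Visit 8 date. The subject has a 9/ET date only, so there is nothing to compare with.
- Result under the literal rule: no event selected, and the subject is scored event-free.

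This conflicts with SAP 19.2.1 (Day 0 to Week 24) and with Protocol 10.3.2.1 (at least one event over the study period). Under either, a Week 6 event counts.

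**2. The plan's own precision figures (Table ABEX.3, N = 250).** Half-width = 1.96 × √(p(1 − p)/n).

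- p = 0.11: 1.96 × √(0.11 × 0.89/250) = 3.88 points, limits 7.1% to 14.9%. Matches.
- p = 0.30: 1.96 × √(0.30 × 0.70/250) = 5.68 points, limits 24.3% to 35.7%. Matches.

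**3. Cost per affected subject.** 1/250 = 0.4 percentage points.

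**4. Range.** Planned drop-outs are 0.20 × 250 = 50. The documents do not say how many will lack a Visit 8 date or how many of those will have had an event, so both are assumptions here. Events lost = (leavers without Visit 8) × (incidence among them), rounded to whole subjects. The base cases are 28/250 = 11.2% (exact 95% interval 7.6 to 15.8) and 75/250 = 30.0% (24.4 to 36.1), the whole-number equivalents of the plan's 11% and 30%.

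| Base | Leavers without Visit 8 | Incidence among leavers | Subjects lost | Reported incidence | Exact 95% interval |
|---|---|---|---|---|---|
| 28/250 | any | none with an event | 0 | 11.2% | 7.6 to 15.8 |
| 28/250 | 50 | half of 11% | 2.75, so 3 | 25/250 = 10.0% | 6.6 to 14.4 |
| 28/250 | 50 | 11% | 5.5, so 6 | 22/250 = 8.8% | 5.6 to 13.0 |
| 75/250 | any | none with an event | 0 | 30.0% | 24.4 to 36.1 |
| 75/250 | 50 | half of 30% | 7.5, so 8 | 67/250 = 26.8% | 21.4 to 32.7 |
| 75/250 | 50 | 30% | 15 | 60/250 = 24.0% | 18.8 to 29.8 |

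The half-incidence rows stand for leavers with shorter time at risk.

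**5. Against the planned precision.** The worst-case losses are 11.2 − 8.8 = 2.4 points and 30.0 − 24.0 = 6.0 points. As fractions of the half-width these are 2.4/3.88 = 0.62 and 6.0/5.68 = 1.06. In the 30% case the reported 24.0% falls below the plan's own lower limit of 24.3%.

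**The case against.** **It is only a programming clarification.** The protocol and SAP 19.2.1 both make the intention clear, and a careful programmer would keep a Week 6 event. That is fair, and it is why the loss is conditional. But SAP 19.1.1 is the text the program will be written from, and no other line overrides it.

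**Visit windowing may supply the date.** SAP 7.1 provides for remapping visits to nominal windows. This could help a subject whose exit visit falls within 7 days of Day 168. It does nothing for one who left in Week 8.

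**The events are not hidden.** The end-of-study counts and rates (SAP 20.1.2, 20.2.2) run to the Visit 9 date, which for a leaver can be the ET date, and all hypoglycaemic events are listed by subject. This stands: a reader could notice the discrepancy. It does not correct the primary percentage, because SAP 20.1.3 keeps the longer window for rates. The per-protocol repeat does not help either, since its criterion (b) is "Have not discontinued from the study prior to 24 weeks".

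**The size is a worst case.** This also stands. Leavers have less time at risk, and a subject lost between Weeks 24 and 28 does have a Visit 8 date.

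**A stronger reading that a reader might infer.** The withdrawal ground in Protocol 8.2 could be said to bias the primary endpoint in itself, because someone withdrawn for increased risk before any qualifying reading is scored event-free. The documents do not support calling that a defect. Incidence under the protocol's own safety rules is a legitimate quantity, and no comparison test depends on it (SAP 7.4). The number of such exits may be zero. The protocol also acts before exit: a 2-unit reduction below 80 mg/dL and up to 4 units after hypoglycaemia (7.1), sulphonylurea adjustment (7.7), and possible continuation after a severe event (7.8.3). An extra withdrawal-reason category or an upper-bound row for these exits would be optional disclosure.

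**Conclusion.** The point holds as a gap in the SAP's derivation. As written, the primary window has no end date for a subject without a Visit 8, and literal application turns recorded events in leavers into non-events while leaving those subjects in the denominator. The same holds for the secondary incidences in SAP 20.1.3.

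The direction is certain if the rule is coded literally: the incidence can only fall. The size is not. It is 0.4 points per affected subject, and nothing if no leaver without a Visit 8 had an event. It reaches 2.4 points (11% case) or 6.0 points (30% case) only if all 50 planned drop-outs lack a Visit 8 date and have the full-period incidence. The study's validity is not in question, and no claim is made about subjects withdrawn for risk without a qualifying reading.

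**What to change.** In SAP 19.1.1 and 20.1.3, define the window end as the Visit 8 date or, if there is no Visit 8, the study exit (ET) date, not later than the end of the Week 24 visit window. State that cap as the Visit 2 date plus 175 days (168 + 7, counting Visit 2 as day 0 as in SAP Table 7.1). A completer's Visit 8 may fall up to 7 days after Day 168, so this cap gives leavers and completers the same outer limit. The Week 24 rates in SAP 20.1.2 use the same cut-off and should carry the same line.

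The cost is one sentence in each derivation, with no new data. There are two downsides. The exit visit can come after the last dose, so some off-drug days may be included for leavers. The reported incidence may also be slightly higher than under the literal rule.

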## 8.3. Lost to Follow-Up

A subject will be considered lost to follow-up if he or she repeatedly fails to return for scheduled visits and is unable to be contacted by the study site. Site personnel are expected to make diligent attempts to contact subjects who fail to return for a scheduled visit or were otherwise unable to be followed up by the site.

## 9. Study Assessments and Procedures

Section 2 lists the Schedule of Activities, with the study procedures and their timing (including tolerance limits for timing).

Appendix 2 lists the laboratory tests that will be performed for this study.

Appendix 5 provides a summary of the maximum number and volume of invasive samples, for all sampling, during the study.

Unless otherwise stated in the subsections below, all samples collected for specified laboratory tests will be destroyed within 60 days of receipt of confirmed test results.

### 9.1. Efficacy and Safety Assessments

#### 9.1.1. Primary Safety Assessments

##### Hypoglycemia

Information on treatment-emergent hypoglycemic events starting from Visit 2 until the last study visit (Visit 9 or early termination [ET] visit) will be collected. Subjects will be trained about signs and symptoms of hypoglycemia. Subjects will be trained to check and record their blood glucose levels if they experience symptoms suggestive of hypoglycemia. For each hypoglycemic event, subjects should record the following data in the study diaries provided by the sponsor via the investigator:

- blood glucose levels
- associated symptoms
- treatment, and
- other pertinent information.

A hypoglycemic event is defined as any time a subject feels that he or she is experiencing a sign or symptom that is associated with hypoglycemia or has a FBG level of  $\leq 54$  mg/dL (3.0 mmol/L), even if it was not associated with signs, symptoms, or treatment consistent with current guidelines.

**Severe hypoglycemia:** An event requiring assistance of another person to actively administer carbohydrates or glucagon or taking other corrective actions. Blood glucose concentrations may not be available during an event, but neurologic recovery following the return of blood glucose to normal levels is considered sufficient evidence that the event was induced by a low blood glucose concentration.

**Nocturnal hypoglycemia:** Any total hypoglycemic event that occurs after bedtime and prior to the first meal in the morning.

**Documented symptomatic hypoglycemia:** An event during which typical symptoms of hypoglycemia are accompanied by a blood glucose level of  $\leq 54$  mg/dL ( $\leq 3.0$  mmol/L) as confirmed by blood glucose measurement.

**Asymptomatic hypoglycemia:** Any event not accompanied by typical symptoms of hypoglycemia but a measured a blood glucose level of  $\leq 54$  mg/dL ( $\leq 3.0$  mmol/L) was observed.

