### **5.2. Number of Participants**

Assuming a 15% screen failure rate, approximately 295 subjects will be screened, so that 250 subjects can be enrolled. Assuming a drop-out rate of 20%, the target is to have a minimum of 200 subjects completing the present study.

In the India subpopulation of ELEMENT 5 study, 5 of the 46 insulin-naïve subjects experienced at least 1 hypoglycemic event (total hypoglycemia incidence with glucose levels  $\leq 54$  mg/dL [3.0 mmol/L]) during the overall study period. When considering the total ELEMENT 5 population, 146 out of 489 subjects (30%) experienced at least 1 hypoglycemic event during the overall study period. Based on these estimates, the precision with 250 and 200 subjects would be as outlined in [Table ABEX.3](#) (95% confidence interval for proportion shown based on normality assumption).

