### **10.3.2. Safety Analyses**

#### **10.3.2.1. Hypoglycemic Events**

The primary endpoint of this study is the incidence of total (symptomatic or asymptomatic with FBG level  $\leq 54$  mg/dL [3.0 mmol/L]) hypoglycemic events at Week 24. The events will be analyzed as following as number and percentage of subjects experiencing at least 1 event over the study period. A 95% confidence interval for the rate will be calculated using the normality assumption.

The rate of total (symptomatic or asymptomatic with FBG level  $\leq 54$  mg/dL [3.0 mmol/L]) hypoglycemic events will be analyzed as follows:

- Number of hypoglycemic events per subject over the study period will be analyzed as continuous variables as per Section 10.3.1 (mean, median, SD, standard error [SE], minimum, and maximum)
- The rate of hypoglycemic events per 30 days, and the rate per year, that is the number of hypoglycemic events per subject year (365.25 days), will be calculated.
  - The rate per 30 days between 2 time points (end of treatment/study vs. baseline) is defined as the total number of events between the time points divided by the actual number of days between the time points, and then multiplied by 30. A similar approach is then used for the number of events per subject-year (365.25 days).
  - These measures will be summarized for the overall study period and will be assessed using a negative binomial model with baseline HbA1c as covariate and the log of the study treatment exposure time as offset variable.

The following types of hypoglycemia (see Section 9.1.1) will be analyzed similarly (incidence and rates) as specified for total hypoglycemia:

- nocturnal hypoglycemia
- severe hypoglycemia
- documented symptomatic hypoglycemia, and
- asymptomatic hypoglycemia

All analyses for the hypoglycemic events will be repeated for the PPS population.

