3.1 Primary endpoints

 Incidence of total (symptomatic or asymptomatic with FBG level of ≤54 mg/dL [≤3.0 mmol/L]) hypoglycemic events at Week 24

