18.2 Analysis

| Population: | FAS and PPS |
|-----------------|---------------------|
| Stratification: | Table: By visit |
| | Listing: By subject |

Statistics: Descriptive statistics (n, mean, standard deviation, standard error, median, minimum, maximum) will be calculated for all the vital signs variables (Actual and change from baseline) for table. Listing will be presented for all the vital signs parameter by subject.

> The change from baseline values to Week 24 will be analysed using the general linear model, with the baseline value of the response variable as covariate after applying the LOCF method to missing values.

> Missing data imputation will be performed as mentioned in section 8.2 point 1.

Efficacy tables will be presented for with and without imputed values separately for each population.

The estimate, 95% confidence interval and p-value will be summarised for efficacy table.

The regression line for the general linear model without categorical variable is as follows:

 $Y = \alpha + \beta (X)$

Where,

Y= The response change in respective vital signs parameter.

 $\alpha = Intercept$

 $\beta = slope$

X= Covariate i.e. Baseline of respective vital signs parameter The hypothesis is as follows

H0: $\beta = 0$

i.e. There is no statistically significant change in respective vital signs parameter at week 24 from baseline depending on the Baseline of respective vital signs parameter.

V/s

H1: β ≠ 0

i.e. There is statistically significant change in respective vital signs parameter at week 24 from baseline depending on the Baseline of respective vital signs parameter.

The above hypothesis will be tested based on α (alpha)=0.05, if the p-value \geq 0.05 then we will conclude that there is no statistically significant change in respective vital signs parameter at week 24 from baseline i.e. Ho is accepted.

The sample SAS programme is as follows:

proc mixed data=dataset;

model Y= X / s cl;

estimate "Model with Mean of baseline respective vital signs parameter " int 1 vital signs parameter baseline mean /CL;

ods output estimates=output dataset;

run; quit;

19. Primary efficacy assessments

The primary endpoint parameter is mention below

- 19.1 Variables and derivations
- 19.1.1 Incidence of total (symptomatic or asymptomatic with FBG level of ≤54 mg/dL [≤3.0 mmol/L]) hypoglycaemic events at Week 24

Variables:

- What was the blood glucose level (mg/dL) prior to treating the event? (In eCRF "Hypoglycemia Events" form)

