- Were signs/symptoms of hypoglycemia present, other than the blood glucose reading? (In eCRF "Hypoglycemia Events" form)
- Hypoglycemic event start date
- Date of Visit 2 (Week 0)
- Date of Visit 8 (Week 24)

Derivation:

- Hypoglycemic event start date ≥ Date of Visit 2 (Week 0) and Hypoglycemic event start date ≤ Date of Visit 8 (Week 24) for accessing the hypoglycemic events from Day 0 to week 24.
- "Symptomatic Hypoglycaemic events" if, the question "What was the blood glucose level (mg/dL) prior to treating the event" result is less or equal to 54 mg/dL and the question "Were signs/symptoms of hypoglycemia present, other than the blood glucose reading" is answered as "YES".
- "Asymptomatic Hypoglycaemic events" if, the question "What was the blood glucose level (mg/dL) prior to treating the event" result is less or equal to 54 mg/dL and the question "Were signs/symptoms of hypoglycemia present, other than the blood glucose reading" is answered as "NO" or "UNKNOWN.

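### The primary hypoglycemia event is labelled by fasting glucose but derived from any glucose, conflicts with protocol 9.1.1, and omits severe events that have no reading

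*Protocol*

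**What the plan says.** **Endpoint wording.** SAP 3.1 gives the primary endpoint as "Incidence of total (symptomatic or asymptomatic with FBG level of ≤54 mg/dL [≤3.0 mmol/L]) hypoglycemic events at Week 24". Protocol 10.3.2.1 agrees: "The primary endpoint of this study is the incidence of total (symptomatic or asymptomatic with FBG level" at or below 54 mg/dL. The synopsis, Table ABEX.2, protocol 10.3.1 and the heading of SAP 19.1.1 also use fasting blood glucose (FBG).

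**SAP derivation.** Under that heading, SAP 19.1.1 uses the eCRF item "What was the blood glucose level (mg/dL) prior to treating the event". An event qualifies when the "result is less or equal to 54 mg/dL and the question" on symptoms is answered yes (symptomatic) or no/unknown (asymptomatic). There is no fasting condition, and the listed variables include no fasting indicator.

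**Protocol 9.1.1.** Under Primary Safety Assessments, the general definition reads "A hypoglycemic event is defined as any time a subject feels that he or she is experiencing a sign or symptom" associated with hypoglycemia, or has an FBG at or below 54 even without symptoms. The subtypes that follow use blood glucose, not FBG. Asymptomatic hypoglycemia, for example, is "Any event not accompanied by typical symptoms of hypoglycemia but a measured a blood glucose level of" 54 mg/dL or lower. The severe subtype says that a reading may not be available and accepts neurologic recovery once glucose normalizes as sufficient evidence.

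**Planning data.** Protocol 5.2 describes the 5/46 rate as "total hypoglycemia incidence with glucose levels" at or below 54. The 146/489 sentence gives no threshold.

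**Change control.** Protocol 10.3.1 requires an amendment for changes to a principal feature, and a description with justification in the SAP or study report for other analysis changes. SAP section 5 only defers deviations to the study report. It does not mention a move from FBG to any glucose.

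**The concern.** This is the only primary endpoint of a single-arm, descriptive safety study, so the incidence is the primary result and the event definition determines it. Three rules stand in the documents, they count different subjects, and nothing reconciles them. A reader who takes the label at face value would think that daytime and 3 am lows were excluded, when the SAP counts them. A reader of protocol 9.1.1 would expect symptomatic events without a qualifying reading to be included, when the SAP leaves them out.

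The severe events matter most for safety. Protocol 9.2.1 makes severe hypoglycemia a serious adverse event. SAP 19.1.1 and 20.1.3 both require a glucose at or below 54. A severe event with no reading would therefore be missing from the primary result and from the severe-hypoglycemia incidence and rates.

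**Working it through.** **1. The plan's precision table.** SE = sqrt(p(1-p)/n); half-width = 1.96 x SE (Table ABEX.3).

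| n | p | SE | Half-width | 95% limits |
|---|---|---|---|---|
| 250 | 11% | 1.98 | 3.88 | 7.1-14.9 |
| 250 | 30% | 2.90 | 5.68 | 24.3-35.7 |
| 200 | 11% | 2.21 | 4.34 | 6.7-15.3 |
| 200 | 30% | 3.24 | 6.35 | 23.65-36.35 |

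All four rows reproduce within rounding. The inputs are 5/46 = 10.87% and 146/489 = 29.86%.

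**2. The three rules side by side.** Column A takes the FBG limit to cover both event types, as the comma in the synopsis implies.

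| Event | A: endpoint wording | B: SAP 19.1.1 | C: protocol 9.1.1 general definition |
|---|---|---|---|
| Fasting reading ≤54 | counted | counted | counted |
| Non-fasting reading ≤54, symptoms | not | counted | counted |
| Non-fasting reading ≤54, no symptoms | not | counted | not |
| Symptoms, reading above 54 | not | not | counted |
| Symptoms, no reading | not | not | counted |

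Provided that fasting lows are entered on the hypoglycemia form, A is a subset of B. Neither B nor C contains the other. Table ABEX.2, protocol 10.3.2.1 and SAP 3.1 lack the comma, so their wording can also be read with the limit on asymptomatic events only, which is close to C.

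**3. Which rule fits the rest of the plan.**
- B is essentially the union of the protocol's documented symptomatic and asymptomatic subtypes. Under A, those subtypes could exceed the total that should contain them.
- Subjects are told to test when symptomatic at any hour, and the 7-point profile includes a 3 am value. A would discard these non-fasting lows.
- Mandatory daily FBG ends at Week 12, but the endpoint runs to Week 24.
- The 5/46 rate is worded on glucose levels, which fits B.

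**4. Possible size (illustration only).** The documents give neither the fasting share nor the share of symptomatic events without a reading ≤54. Assumed inputs, n = 250, Clopper-Pearson limits as in the SAP:

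- B at the 11% planning rate: 250 x 0.11 = 27.5, so 28/250 = 11.2% (7.6-15.8).
- A, if 25%, 50% or 75% of those subjects have a qualifying fasting reading: 7, 14 or 21 subjects, that is 2.8% (1.1-5.7), 5.6% (3.1-9.2) or 8.4% (5.3-12.6).
- C = 27.5 x (1 - a) + 222.5 x g, where a is the share of B subjects with only asymptomatic non-fasting lows and g is the share of the others with symptoms but no reading ≤54. With a = 0 and g = 5%, 10%, 20%: 39, 50, 72 subjects, that is 15.6%, 20.0%, 28.8%. With a = 50%: 25, 36, 58 subjects, that is 10.0%, 14.4%, 23.2%.
- With B at 30% (75/250), the same assumptions give A = 7.6-22.4% and C = 18.4-44.0%.

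The gap between A and B at 11.2% runs from 11.2 - 8.4 = 2.8 points, inside the planned 3.9-point half-width, to 11.2 - 2.8 = 8.4 points, outside it. C can lie above B (28.8%) or slightly below it (10.0%).

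**5. Severe events without a reading.** Each subject affected only by such an event adds 1/250 = 0.4 points to the primary incidence. The number of such subjects is unknown.

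**The case against.** The strongest reply is that only one rule is programmed. SAP 19.1.1 is deterministic and SAP 19.2.1 analyses it. A reader might infer that the headline figure will vary with the section followed. The documents do not support that, because no section programs a fasting-only or symptom-only count.

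The general sentence in protocol 9.1.1 follows the diary instructions and can be read as a rule for what to record. On that reading the conflict shrinks to one mislabel, FBG for blood glucose. The any-hour testing instruction and the nocturnal subtype make a wording slip likely. This is plausible but not stated: the sentence stands under Primary Safety Assessments and does not exclude symptom-only events from the total.

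Three further inferences go too far:
- That both planning rates rest on any glucose ≤54. The threshold is attached only to 5/46, and even there the time of day is not stated.
- That a particular shift, such as 11% falling by half, has been shown. The shares are assumed.
- That unmeasured severe events would vanish from the report. They are serious adverse events by definition and should still appear in those listings; the gap is in the hypoglycemia analyses.

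Finally, there is no success threshold, so no decision rule could flip.

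**Conclusion.** The inconsistency is real and needs to be resolved before reporting. The endpoint label says fasting glucose, the programmed rule uses any glucose, and protocol 9.1.1 counts symptoms with or without a reading, or a fasting low. One number will be produced, but under a label that does not describe it and with no declared change. The programmed rule is the one that best fits the protocol's own subtypes and the 5/46 rate; its match to 146/489 cannot be checked. The loss of severe events without a reading is a separate, substantive gap in that rule.

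The size cannot be derived from the documents. The ranges in the working rest wholly on assumed shares and show only that the choice of rule could move the result by more than the planned half-width. The sample size and the precision arithmetic are not in dispute.

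**What to change.** 1. Replace the FBG threshold with blood glucose at or below 54 mg/dL at any time in the synopsis, Table ABEX.2, protocol 9.1.1, 10.3.1 and 10.3.2.1, SAP 3.1 and the SAP 19.1.1 heading.
2. Amend SAP 19.1.1 and 20.1.3 so that severe events meeting the protocol 9.1.1 definition count even when no reading exists.
3. Add one named sensitivity analysis that adds all symptomatic events without a reading at or below 54, whether the reading is missing or above 54. This reproduces the protocol 9.1.1 general definition once it is reworded as in item 1.
4. Declare and justify the change before database lock.

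The cost is wording and one extra table. The eCRF already has fields for glucose, symptoms and need for assistance, so no new data are required. Because the primary endpoint text changes, the sponsor must decide under protocol 10.3.1 whether this alters a principal feature and so needs an amendment, with the associated ethics documentation.
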